### **6.3. Study Follow-up Phase**

#### **6.3.1. Follow-up 7 days**

Following a subject's final PMT administration or following enrollment in the non-PMT arm, subjects enter the follow up phase. During this phase, vital signs, symptoms, and laboratory values suggestive of adverse events will be tracked and recorded. Specifically, while remaining inpatient, daily maximum temperature, number of bowel movements, and any episodes of emesis will be recorded (based on electronic medical record) for 7 calendar days post-FMT or post-enrollment in non-PMT arm. In preparation for discharge, subjects will be given a diary for tracking daily temperature, number of bowel movements, and any episodes of emesis for 7 days post last FMT or post-enrollment (subjects will be given a symptom diary card; a digital thermometer will also be provided). Subjects will be contacted by telephone or in-person for an interview focused on potential adverse events at 7 days after final FMT or post-enrollment for non-PMT arm; the first attempt at contact will be made by the first working day at 7 days or later (not to exceed 10 days) following the final FMT. (In case of telephone follow-up, the 7-day symptom diary card will be transcribed by study staff over the phone/and or collected during the in-person follow-up visit. See [Section 6.3.2](#)). Telephone versus in-person follow-up will be determined based on subject preference. If subjects prefer to be seen in person, but have been discharged from the hospital, a clinic visit with a study team member will be arranged.

To address the exploratory aims, daily swabs of available stool and peri-rectal swabs will be taken for microbiome analysis for 7 days post-FMT or post-enrollment for non-PMT arm. If blood that was collected for clinical purposes would otherwise be discarded, it will be captured for immune response phenotyping. Stool specimens will be obtained by placing flocced nylon swabs in stool if available (e.g. in bag of fecal management system). In addition, peri-rectal swabs will be obtained if possible. Blood will be collected from residual material available in EDTA ("purple top") vacutainer tubes already collected in the clinical laboratory. If subjects have been discharged from the hospital, no swabs will be collected. If no residual blood is available, or if subjects have been discharged from the hospital, no blood will be collected. Stool, peri-rectal and blood specimen analysis will be directed by the principal investigator and study team.

**6.3.2. Follow-up 30 days**

Subjects will be contacted again by telephone or in-person at 30 days (+/- 3 days) after final FMT or post-enrollment for non-PMT arm for an interview focused on potential adverse events. Telephone versus in-person follow-up will be determined based on subject preference. (If subjects prefer to be seen in person, but have been discharged from the hospital, a clinic visit with a study team member will be arranged).

**6.3.3. Follow-up 90 days**

Subjects will be contacted by telephone or in-person at 90 days (+/- 7 days) after final FMT or post-enrollment for non-PMT arm for an interview focused on potential adverse events. Telephone versus in-person follow-up will be determined based on subject preference. (If subjects prefer to be seen in person, but have been discharged from the hospital, a clinic visit with a study team member will be arranged).

**6.3.4. End-of-study visit at 180 days**

The study will conclude after subjects are contacted by telephone or in-person at 180 days (+/- 10 days) after final FMT or post-enrollment for non-PMT arm for a final interview focused on potential adverse events. Telephone versus in-person follow-up will be determined based on subject preference. (If subjects prefer to be seen in person, but have been discharged from the hospital, a clinic visit with a study team member will be arranged).

Subjects will be permitted to initiate electronic communication with the study team, although planned follow up visits will be conducted by telephone or in person. The study team may reach out to subjects electronically if difficulties arise in reaching the subject by telephone in order to schedule visits, but study-related questions will not be asked electronically. Subjects will be classified as lost to follow up if at least three attempts are made at contact without success; however, medical record review will still be used to obtain follow up information on these subjects. If a subject is eligible and enrolled a second (or greater) time, then their subsequent follow up will be conducted according to the schedule set by their most recent enrollment, and any remaining follow ups from earlier enrollment(s) will not be performed.

**6.4. Rescue Therapy**

If a subject is thought to have a severe adverse event it will be recorded by the study team and the subject will be followed until resolution and referred to subject's primary clinical care team. In the case of an inadequate clinical response, the subject's primary clinical care team will be contacted, so that the subject can pursue treatment at their discretion. Regardless of rescue therapy used, subjects will continue to be followed until the end of the study.

**6.5. Unscheduled Visits**

Data collected from subjects who contact the study team (by telephone, electronically, or in-person) outside of the scheduled visits (as above) will be associated with the next scheduled study visit, as each study visit is intended to retrospectively cover the time period since the last study visit.

## **6.6. *Subject Withdrawal***

Subjects may withdraw from the study at any time without impact to their regular medical care, but they will receive no further treatment with investigational product. They may also be discontinued from the study at the discretion of the Investigator for lack of adherence to intervention or study procedures or visit schedules, adverse events, or due to other concerns. The Investigator or the Sponsor may withdraw subjects who violate the study plan, or to protect the subject for reasons of safety or for administrative reasons. It will be documented whether or not each subject completes the clinical study. The targeted study enrollment is 90 subjects randomized; subjects who withdrawal after randomization will not be replaced.

### **6.6.1. *Data Collection***

Data will be obtained from direct subject observation, review of the subject's electronic medical record, scheduled and unscheduled follow-up visits (which may be in-person or by telephone), as detailed above. For subjects who withdraw consent to participate in the study, data collected up until the time of withdrawal will be kept, but no further data will be collected.

### **6.7. *Early Termination Visits***

If the subject decides to withdraw from the study after randomization, the subject will be asked to complete all follow-up activities that would have been performed at the next scheduled follow-up visit.

**Table 3: Schedule of study procedures**

Study Phase	Screening & Enrollment	Intervention	Follow-Up: 30 & 60 minutes	Follow-Up: First 3 Days	Follow-Up: 7 days	Follow-Up: 30 days	Follow-Up: 90 days	Follow-Up: 180 days
Study Days	1	1* (Retreatment Day 4 / 7*)	1* (Retreatment Day 4 / 7*)	Final Intervention +1, +2, +3	Final Intervention +7	Final Intervention +30	Final Intervention +90	Final Intervention +180
Surveillance Test Review	X							
Medical Record Review	X			X	X	X	X	X
Review Inclusion/Exclusion	X							
Informed Consent	X							
Enteral Access Check	X							
Randomization	X							
Dispense PMT to Clinical Site		X						
PMT Receipt Check		X						
PMT Administration		X						
Compliance Check		X						
Vital Signs Review			X	X	X			
Symptom Review			X	X	X	X	X	X
Laboratory Review				X	X	X	X	X
CRF3 / Outcomes Check				X	X	X	X	X
Adverse Event Check		X	X	X	X	X	X	X
Microbiome Swab from Otherwise Discarded Stool				X	X			
Immune Phenotypic Analysis on Otherwise Discarded Whole Blood				X	X			

\*If PMT administration is unable to be performed on days 1, 4 and/or 7, administration and 30/60-minute follow up within 1 calendar day before or after those days will be permitted (for the first administration, administration within 1 calendar day after enrollment will be permitted). If the first administration occurs on day 2, then the second and third administration dates (if eligible) will be days 5 and 8 (+/- 1 calendar day).

## **7. Study Evaluations and Measurements**

### **7.1. Medical Record Review**

The medical record will be reviewed prior to enrollment, in order to assess eligibility, as outlined above. The medical record will be reviewed at 3-day, 7-day, 30-day, 90-day, and 180-day follow-ups to help ascertain primary and secondary outcomes, as well as adverse events (Sections 3.2 and 9.1.3). HIPAA authorization will be obtained with informed consent.

### **7.2. Physical Examination**

Physical examination will include only of vital sign measurements, as below.

### **7.3. Vital Signs**

Vital signs will be checked by study team personnel during the 60 minute observation period after product administration. Parameters for notifying the clinical care team of abnormalities are outlined in the study intervention phase section above (Section 6.2.3). Vital signs will be checked while subjects are either sitting or lying down, as per their preference.

### **7.4. Laboratory Evaluations**

No laboratory evaluations will be performed as a part of this study. Laboratory values will be collected from review of the subject's electronic medical record, in order to ascertain outcome data and adverse events, as described above.

### **7.5. Pregnancy Testing**

Urine pregnancy testing using an FDA-cleared test will be performed as a part of this study.

### **7.6. Other Evaluations, Measures**

Subjects will be provided with a diary and thermometer to keep track of their temperature (once a day), stool frequency, and any emesis. This diary will be reviewed with subjects at their 7-day follow-up visit.

For the exploratory aim, stool microbiome analysis will be performed on stool samples and peri-rectal swabs. Likewise, immune phenotypic analysis using flow cytometry may be performed on a subset of subjects using whole blood collected for clinical purposes, which would otherwise be discarded. Stool specimens will be obtained by placing flocced nylon swabs in available stool. Peri-rectal swabs will be obtained if possible. Blood will be collected from residual material available in EDTA ("purple top") vacutainer tubes already collected in the clinical laboratory.

### **7.7. Efficacy Evaluations**

The primary outcome (time to resolution of S/SC/F-CDI symptoms) will be satisfied when the criteria listed in Section 3.2.1 are met for 72 hours or when the subject is discharged from the hospital (not to hospice or palliative care). The criteria will be assessed via electronic medical record review as per Section 3.2.1.

### 7.8. *Genetic Testing (only if applicable)*

No human genetic testing will be performed. For the exploratory aim, stool microbiome analysis will be performed on stool samples and peri-rectal swabs obtained as described in [Section 7.6](#). This will involve sequencing of microbial nucleic acids. This will not involve human DNA sequencing and thus does not comprise genetic testing. Likewise, phenotyping of immune response via flow cytometry may be performed on a subset of subjects, using whole blood collected for clinical purposes that would otherwise be discarded. This will not involve human DNA sequencing and or genetic testing.

### 7.9. *Safety Evaluations*

#### 7.9.1. **Deviations and Exceptions**

##### **Exception** (Prospective action):

An *exception* is defined as a one-time, intentional action or process that departs from the approved study protocol, intended for one occurrence. If the action disrupts the study progress, such that the study design or outcomes may be compromised, or the action compromises the safety and/or welfare of study subjects, advance documented approval from the Regulatory Sponsor and local regulatory review committees, per institutional guidelines, is required. Approval from the Regulatory Sponsor must be received prior to submission to the local regulatory review committees.

##### **Deviation** (Retrospective action):

A *deviation* is defined as a one-time, unintentional action or process that departs from the approved study protocol, involving one incident and identified retrospectively. If the deviation disrupts study progress, such that the study design or outcomes may be compromised, or the deviation compromises the safety and/or welfare of study subjects, the deviation must be reported to the Regulatory Sponsor within 2 days of PI knowledge and to local regulatory review committees per institutional guidelines.

Report the following information on the Sponsor's exception/deviation form:

- Protocol number
- Subject number
- Description of the exception or deviation
- Impact on subject safety
- Impact on data integrity

Deviations that are assessed by the PI to not disrupt the study progress, such as not affecting the study design or outcome, or compromising the safety and/or welfare of study subjects, should be documented in site records and contain documentation of the PI's assessment.

#### 7.9.2. **Safety Parameters**

Safety will be monitored in several ways:

- 30- and 60-minute observations with vital sign checks after investigational product administration.
- Follow-up daily for 3 days and at 7 days, 30 days, 90 days, and 180 days as outlined in the schedule of study procedures ([Table 3](#)).
- Examination of safety-related secondary outcomes, including: bacteremia, mortality, hospital admission, colectomy or diverting ileostomy.

## **8. Statistical Plan**

### **8.1. Primary Endpoint**

The primary outcome is time to resolution of symptoms associated with S/SC/F-CDI. The primary outcome will be satisfied when the subject is discharged from the hospital (not to hospice or palliative care) or, while the subject remains hospitalized, when the criteria listed in [Section 3.2.1](#) are satisfied for 72 hours.

### **8.2. Secondary Endpoints**

Secondary endpoints are detailed in [Section 3.2.2](#). Secondary endpoints will include all-cause mortality (30- and 60-days following enrollment), colectomy or diverting ileostomy within 30 days after enrollment, cumulative days of hospitalization from enrollment until 30 days after enrollment, cumulative days in intensive care unit from enrollment until 30 days after enrollment, bacteremia from enrollment until 30 days after enrollment, readmission within 60 days of discharge from index hospitalization.

### **8.3. Exploratory Endpoints**

Exploratory endpoints will include: (1) the baseline gut bacterial community composition and host immune phenotype associated with S/SC/F-CDI, (2) the change in gut bacterial community composition and host immune phenotype associated with each of the above treatment strategies, and (3) the relationship between baseline gut bacterial community composition, host immune phenotype, and treatment outcome in patients with S/SC/F-CDI.

## 8.5. Statistical Methods

### 8.5.1. Baseline Data

Baseline and demographic characteristics, as well as vital signs, laboratory values, and radiologic study results, will be summarized by standard descriptive statistics (including mean and standard deviation for continuous variables such as age and standard percentages for categorical variables such as gender). Collected variables will include but not be limited to: body mass index (BMI), comorbid medical conditions, use of immunosuppressive medications, use of proton pump inhibitor (PPI) or H2 antagonist medications, use of concurrent non-CDI directed antibiotics, hospital length of stay and level of care. Time between CDI diagnosis and intervention will also be assessed.

### **8.5.2. Efficacy Analysis**

A modified intention-to-treat (m-ITT) analysis will be performed for the primary outcome of time to CDI resolution (endpoint outlined above). In the m-ITT analysis, subjects who die following randomization but before receiving their first FMT will be excluded. A competing risks survival model will be used to compare the FMT (aggregate) and no-FMT groups. A p-value (one-sided) of  $<0.2$  will be considered significant.

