**Statistical Methodology**

Primary outcome will be time to resolution of severe symptoms. We will compare both FMT groups (i.e., upper and lower gastrointestinal administration) in aggregate versus the standard of care group via competing risk regression model.

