## **3. Investigational Plan**

### **3.1. General Design**

We will perform a randomized, controlled, open label trial. Subjects will be screened to evaluate if they meet inclusion criteria for severe or severe complicated/fulminant CDI. If eligible, subjects will participate in the informed consent process. Following informed consent, subjects

will be randomized to one of three arms: (1) standard of care antibiotics (no intervention), (2) PMT-upper GI administration plus standard of care antibiotics, or (3) PMT-lower GI administration plus standard of care antibiotics. Subjects will then be eligible to receive up to two additional administrations of PMT (upper or lower GI) at 3-day (+/- 1 day) intervals if they do not meet pre-defined criteria for clinical improvement (see [Section 3.2.1](#) below). Subjects will be followed until 180 days after their last PMT dose.

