**Figure 1: Allocation to Interventional Group Flow Diagram**

### 3.2. Study Endpoints

#### 3.2.1. Primary Study Endpoints

The primary outcome is resolution of symptoms associated with S/SC/F-CDI, listed below. The primary outcome will be satisfied when the subject is discharged from the hospital (not to hospice or palliative care) or, while the subject remains hospitalized, when the following criteria are met for 72 hours:

- If radiology study or studies performed, ileus/dilation/megacolon either not noted or noted as resolved (electronic medical record search words: “ileus”, “dilated”, “dilation”, or “megacolon”)
- Ileus/megacolon either noted as resolved by any provider documentation or not noted (electronic medical record search words: “ileus”, “megacolon”)
- WBC < 15,000 cells/uL
- Serum creatinine decreased, unchanged, or increased by  $\leq 0.2$  mg/dL over 72 hours (if not receiving continuous renal replacement therapy (CRRT) or hemodialysis (HD))
- Lactate  $\leq 2.2$  mmol/L (if measured by clinical care team)
- No vasopressors used (including epinephrine, norepinephrine, phenylephrine, or vasopressin)
- Temperature  $< 38.5$  °C and  $\geq 35.6$  °C
- < 8 bowel movements per day and < 600 mL unformed stool (if volume recorded)
- Meeting fewer than 3 systemic inflammatory response syndrome (SIRS) criteria (i.e., no more than two of the following: heart rate > 90 beats per minute; respiratory rate > 20 breaths per minute or PaCO2 < 32 mmHg; temperature > 38°C or < 36°C; WBC > 12,000 cells/uL, < 4,000 cells/uL, or > 10% immature (band) forms)

Discharge to hospice, need for bowel surgery (colectomy, diverting ileostomy), and death will count as failures. Subjects who undergo bowel surgery after initial PMT administration will not be eligible for additional administrations.

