## **8.6. *Subject Population(s) for Analysis***

For the primary analysis, a modified intention-to-treat (mITT) population will be used, in which subjects who die following randomization but before receiving their first FMT will be excluded. Secondary intention-to-treat and per-protocol analyses will also be performed. All randomized subjects will be included in the latter analyses.

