## **12. Ethical Considerations**

This study is to be conducted in accordance with applicable US government regulations and international standards of Good Clinical Practice, and applicable institutional research policies and procedures.

This protocol and any amendments will be submitted to a properly constituted independent Ethics Committee (EC) or Institutional Review Board (IRB), in agreement with local legal prescriptions, for formal approval of the study conduct. The decision of the EC/IRB concerning the conduct of the study will be made in writing to the investigator and a copy of this decision will be provided to the sponsor before commencement of this study.

Protocol modifications, except those intended to reduce immediate risk to study subjects, may be made only by the University of Pennsylvania and the Sponsor. A protocol change intended to eliminate an apparent immediate hazard to subjects may be implemented immediately, provided the IRB/IEC is notified within 5 days.

Any permanent change to the protocol must be handled as a protocol amendment. The written amendment must be submitted to the IRB/IEC and the investigator must await approval before implementing the changes. The Sponsor will submit protocol amendments to the appropriate regulatory authorities for approval.

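### The primary m-ITT population drops deaths before the first FMT, a rule that as intended removes failures from the FMT arm only and, under a Fine-Gray type model, raises the false-positive rate

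*Combined protocol and SAP*

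**What the plan says.** Section 8.5.2 sets the rule for the primary efficacy analysis: "In the m-ITT analysis, subjects who die following randomization but before receiving their first FMT will be excluded". Section 8.6 repeats it and confirms its status: "For the primary analysis, a modified intention-to-treat (mITT) population will be used". ITT and per-protocol analyses are secondary.

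Section 3.2.1 fixes how death is scored: "Discharge to hospice, need for bowel surgery (colectomy, diverting ileostomy), and death will count as failures". Under Section 3.1 the control arm receives antibiotics without the product, so no first FMT exists in that arm. Table 3 limits the time before dosing: "for the first administration, administration within 1 calendar day after enrollment will be permitted".

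The Study Summary says the two FMT groups are compared "in aggregate versus the standard of care group via competing risk regression model". Section 8.5.2 also refers only to a competing risks model. Neither place says whether the model is Fine-Gray (subdistribution hazard) or cause-specific. The test is one-sided at 0.2.

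**The concern.** Membership of the primary population depends on a post-randomization event that is itself a failure of the primary endpoint. The cutoff for that event, the first FMT, exists in one arm only. Take two subjects, one per arm, who die at the same hour on day 1. On the intended reading the FMT-arm subject leaves the analysis and the control stays in as a failure. No matching time window is set for controls.

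Nor does the rule define a treated population. An FMT-arm subject who goes to surgery or hospice before dosing, or who is never dosed for another reason, stays in. Only deaths leave.

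The prespecified significance decision would then rest on a comparison that is no longer as randomized and, as intended, can move only toward FMT. The wording also does not say that control deaths are kept, so the rule is undefined for that arm.

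**Working it through.** **Inputs from the protocol.** 90 subjects (4.5), 2:1 to FMT (3.1.6), so 60 v 30. One-sided 0.2 (8.5.2). Death is a failure (3.2.1). First dose on day 1 or one calendar day later (Table 3). The 4-day duration is one of the baseline scenarios in 8.4.

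**Assumptions.** The protocol gives no mortality rate. The share failing was set at 15% or 25% of each arm. Resolution times are exponential with median 4 days.

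**The plan's own figures.** The plan states no false-positive rate beyond the 0.2 threshold. Its power figures can be checked with the Schoenfeld approximation, power = Φ(√(d·p(1−p))·ln HR − z), with d = 90 events and p = 1/3, so √(90 × 2/9) = 4.472:
- 4 to 2 days, HR 2: 4.472 × 0.693 − 1.282 = 1.818, power 0.965 (stated 0.97).
- 7 to 4 days, HR 1.75: 4.472 × 0.560 − 1.282 = 1.221, power 0.889 (stated 0.90).

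Both agree within two points, using the two-sided 0.2 critical value. These figures count all 90 subjects and allow for no exclusions.

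**How many exclusions to expect.** If all failures were deaths spread evenly over 30 days:
- 15% failing: 60 × 0.15 = 9 deaths, 9/30 = 0.3 per day, so 0.3 to 0.6 in a 1 to 2 day window.
- 25% failing: 60 × 0.25 = 15 deaths, 15/30 = 0.5 per day, so 0.5 to 1.0.

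A constant hazard with 30-day mortality of 10% to 30% gives 0.2 to 1.4. About 0 to 2 exclusions is realistic. Three would need front-loaded deaths.

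**Why the model matters.** The score test is Z = U/√V with U = Σ(D₁ − D·R₁/R), where D₁ and R₁ are FMT-arm resolutions and numbers at risk, and D and R are the totals. Under Fine-Gray with complete follow-up, failures remain in the risk set. Dropping an FMT-arm death then lowers R₁ at every later resolution without lowering D₁, so U rises. Under a cause-specific model that subject leaves the risk set within a day or two anyway, so dropping them changes little.

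**False-positive rate with no true effect.** One-sided 0.2, with pre-dose deaths equally likely in both arms and excluded from the FMT arm only. Fine-Gray: 40,000 trials per cell, Monte Carlo SE about 0.002. Cause-specific: 15,000 trials per cell.

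| Expected exclusions of 60 | Fine-Gray, 15% failing | Fine-Gray, 25% failing |
|---|---|---|
| 0 | 0.195 | 0.198 |
| 0.65 | 0.225 | 0.221 |
| 1 | 0.243 | 0.231 |
| 2 | 0.296 | 0.274 |
| 3 | 0.364 | 0.322 |

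The cause-specific rate is 0.194 to 0.208 in all cells. A separate Fine-Gray run at 0.3 and 0.5 expected exclusions gave 0.212 and 0.217 (15% failing) and 0.204 and 0.216 (25%).

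**On the scale of the endpoint.** With 51 of 60 FMT subjects resolved, ITT gives 51/60 = 85.0%. One exclusion gives 51/59 = 86.4% and two give 51/58 = 87.9%.

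**The literal reading.** Every control who dies does so without a first FMT. If all control deaths are dropped and all failures are deaths, the Fine-Gray false-positive rate falls below 0.01, so the bias runs against FMT.

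**The remedy under the null.** With 1 or 2 expected pre-dose deaths, ITT gives 0.192 to 0.196. Excluding early deaths from both arms gives 0.195 to 0.198.

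**The case against.** The strongest reply is that the inflation depends on two things the plan leaves open. The exclusion sentence names no arm, and its literal reading reverses the bias. The model is not named, and under a cause-specific analysis the effect is negligible. Both points are correct. They make the result conditional but do not rescue the rule: one sentence that can bias the test in either direction cannot stand in the primary population. FMT-only exclusion is the likelier intent, because the literal reading would delete every control death from an endpoint that scores death as failure. Fine-Gray is the likelier model for the same reason, though that too is inference.

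The second reply is size. Dosing follows enrollment closely, and patients on comfort care are not enrolled. The even-spread estimate is 0.3 to 1.0 exclusions, and it treats every failure as a death although surgery and hospice also count. At that level the rate is about 0.20 to 0.24 against a deliberately lenient threshold. This stands: the rates for two exclusions are the upper end of what is realistic, and those for three lie beyond it.

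The third reply is that a secondary ITT analysis is prespecified. It would expose a discrepancy, but the significance decision rests on m-ITT, so it does not control the error of the primary test.

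**Conclusion.** The concern holds. The primary analysis excludes subjects on an outcome that counts as failure, by a criterion that cannot apply equally to both arms. On the intended reading and under a Fine-Gray type model, the bias favors FMT. The one-sided false-positive rate rises from about 0.20 to 0.23–0.24 with one expected exclusion and 0.27–0.30 with two. This rests on assumed failure shares of 15% and 25%, exponential resolution times and equal early mortality in the arms. Under a cause-specific model there is almost no effect. Under the literal wording the direction reverses. The likely size is modest, but the defect is in the primary population and should be corrected.

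**What to change.** In Sections 8.5.2 and 8.6, make ITT the primary population: all randomized subjects, by assigned arm, with time measured from randomization and death as a competing failure. Keep m-ITT only as a sensitivity analysis, with a rule that applies identically to both arms, such as excluding deaths within the permitted first-dose window after enrollment in either arm. Name the competing-risks model.

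A separate correction, which adds no weight to this point, belongs in the same amendment. After listing the ITT and per-protocol analyses, Section 8.6 says "All randomized subjects will be included in the latter analyses". That leaves the per-protocol set undefined, so it needs its own definition.

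The cost is an amendment to the wording of Section 8 with IRB approval, since Section 12 says "Any permanent change to the protocol must be handled as a protocol amendment". No new data are needed, because ITT is already planned. The statistical price is slight dilution by undosed FMT-arm deaths. For a true reduction from 4 to 3 days with 15% failing (20,000 trials), Fine-Gray power with 1 and 2 expected pre-dose deaths is 0.388 and 0.381 under ITT, against 0.394 and 0.401 with symmetric exclusion. The loss is 0.394 − 0.388 = 0.006 and 0.401 − 0.381 = 0.020.
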